Attachment 7: Instruction for Concomitant Medications to be Used with Precaution

Ibrutinib is metabolized primarily by CYP3A. Avoid co-administration with strong or moderate CYP3A inhibitors and consider alternative agents with less CYP3A inhibition. Co-administration of ketoconazole, a strong CYP3A inhibitor, in 18 healthy subjects increased dose normalized exposure, C_{max} and AUC_{0-last}, of ibrutinib by 29- and 24-fold, respectively. The maximal observed ibrutinib exposure (AUC) was \leq 2-fold in 37 patients treated with mild and/or moderate CYP3A inhibitors when compared with the ibrutinib exposure in 76 patients not treated concomitantly with CYP3A inhibitors. Clinical safety data in 66 patients treated with moderate (n=47) or strong CYP3A inhibitors (n=19) did not reveal meaningful increases in toxicities. Strong inhibitors of CYP3A (eg, ketoconazole, indinavir, nelfinavir, ritonavir, saquinavir, clarithromycin, telithromycin, itraconazole, nefazadone, and cobicistat) and moderate inhibitors (eg, voriconazole, erythromycin, amprenavir, aprepitant, atazanavir, ciprofloxacin, crizotinib, darunavir/ritonavir, diltiazem, fluconazole, fosamprenavir, imatinib, verapamil, amiodarone, dronedarone) should be avoided. If the benefit outweighs the risk and a strong CYP3A inhibitor must be used, reduce the ibrutinib dose to 140 mg or withhold treatment temporarily (for 7 days or less). If a moderate CYP3A inhibitor must be used, reduce ibrutinib to 140 mg for the duration of the inhibitor use. No dose adjustment is required in combination with mild inhibitors. Monitor subject closely for toxicity and follow dose modification guidance as needed. Avoid grapefruit and Seville oranges during ibrutinib treatment, as these contain moderate inhibitors of CYP3A.

Coadministration of ibrutinib with strong inducers of CYP3A decreases ibrutinib plasma concentrations by approximately 10-fold. Avoid concomitant use of strong CYP3A inducers (eg, carbamazepine, rifampin, phenytoin, and St. John's Wort). Consider alternative agents with less CYP3A induction.

Examples of inhibitors, inducers, and substrates can be found at <http://medicine.iupui.edu/clinpharm/ddis/main-table/>

Drugs that may have their plasma concentrations altered by ibrutinib

In vitro studies indicated that ibrutinib is a weak inhibitor toward CYP2B6, CYP2C8, CYP2C9, CYP2C19, CYP2D6, and CYP3A4/5. The dihydrodiol metabolite of ibrutinib is a weak inhibitor toward CYP2B6, CYP2C8, CYP2C9, and CYP2D6. Both ibrutinib and the dihydrodiol metabolite are at most weak inducers of CYP450 isoenzymes in vitro. Therefore, it is unlikely that ibrutinib has any clinically relevant drug-drug interactions with drugs that may be metabolized by the CYP450 enzymes.

In vitro studies indicated that ibrutinib is not a substrate of P-gp, but is a mild inhibitor. Ibrutinib is not expected to have systemic drug-drug interactions with P-gp substrates. However, it cannot be excluded that ibrutinib could inhibit intestinal P-gp after a therapeutic dose. There is no clinical data available; therefore, co-administration of narrow therapeutic index P-gp substrates (eg, digoxin) with ibrutinib may increase their blood concentration and should be used with caution and monitored closely for toxicity.

Concomitant Use of Ibrutinib/Placebo and QT Prolonging Agents

Any medications known to cause QT prolongation should be used with caution; periodic monitoring with electrocardiograms (ECG) and electrolytes should be considered and, if needed, the medical monitor may be contacted.

Concomitant Use of Ibrutinib/Placebo and Antiplatelet Agents and Anticoagulants

Warfarin or other vitamin K antagonists should not be administered concomitantly with ibrutinib. Supplements, such as fish oil and vitamin E preparation should be avoided. Use ibrutinib with caution in subjects requiring other anticoagulants or medications that inhibit platelet function. Subjects with congenital bleeding diathesis have not been studied. Ibrutinib should be held at least 3 to 7 days pre- and post-surgery depending upon the type of surgery and the risk of bleeding.

Subjects requiring the initiation of therapeutic anticoagulation therapy (other than warfarin or a vitamin K antagonist) during the course of the study should have treatment with ibrutinib/placebo held, the sponsor's medical monitor should be contacted, and ibrutinib/placebo should not be restarted until the subject is clinically stable and the re-initiation of ibrutinib/placebo is approved by the sponsor's medical monitor. Subjects should be observed closely for signs and symptoms of bleeding. No dose reduction is required when study drug is restarted.

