6.4. Dose Modifications

Treatment modifications may be made to both ibrutinib and nivolumab. Changes in dose apply only to ibrutinib. Nivolumab will be given at fixed dose, treatment modifications are primarily dose delays.

Adjustments of study drug dose should be overseen by the principal- or sub-investigator(s) unless an immediate safety risk is apparent. The dose adjustments are applicable to all subsequent treatment cycles.

Note: The recommendation to discontinue study therapy applies to both study drugs. If appropriate and after consultation with the Sponsor, subjects may receive ibrutinib alone. Following implementation of amendment 7, treatment with single agent ibrutinib will be discontinued and an End of Trial visit will be performed for patients not scheduled to rollover into long-term extension study CAN3001. Patients scheduled to roll over into Study CAN3001 will continue treatment.

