6.4.1. Ibrutinib Dose Modifications

Dose reduction levels for ibrutinib, if required in Section 6.4.3, are listed in Table 7.

Table 7: Dose Reduction for Ibrutinib

| Ibrutinib Dose | 420 mg | 560 mg |
|----------------|--------|--------|
| Dose Level -1 | 280 mg | 420 mg |
| Dose Level -2 | NA | 280 mg |

Ibrutinib dose reductions below 280 mg per day are not permitted and may require discontinuation of study therapy after consultation with the Sponsor. Dose escalations of ibrutinib to the previous higher dose may be considered after consultation with the Sponsor.

In Part A, intra-patient dose escalation may be requested by the investigator and discussed with the medical monitor once a subsequent higher combination dose has been declared acceptable by the SET for subjects who (1) have received at least 4 cycles of combination treatment at the assigned dose level, and (2) have not experienced a DLT or therapy-related SAE. Subjects whose dose has been escalated will not be considered for the safety evaluation in the subsequent dose level and the determination of the RP2D.

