8.10. Infection

Subjects with a documented infectious complication should receive oral or intravenous antibiotics or other anti-infective agents as considered appropriate by the treating investigator for a given infectious condition, according to standard institutional practice.

Usage of antimicrobial prophylaxis in accordance with standard practice (eg, American Society of Clinical Oncology guidelines [Flowers 2013]¹⁹) is permitted and should be considered in subjects who are at increased risk for opportunistic infections.

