9.4. Concomitant Medications to be Avoided, or to be Used with Caution

The bioavailability and in consequence the safety as well as efficacy profile of the medications listed in [Table 20](#) may be altered when co-administrated with study therapy. Therefore, these medications should be avoided, or should be administered with caution concomitantly with study therapy. Instructions for medications to be used with precaution are also provided in [Attachment 7](#).

Table 20: Concomitant Medications to be Avoided or to be Used with Caution

| |
|---|
| CYP3A4 /5 Inducers and Inhibitors |
| 
 • Strong and moderate CYP3A4/5 inducers¹ • Strong and moderate CYP3A4/5 inhibitors¹ • Grapefruit and Seville oranges |
| QT-Prolonging Agents |
| 
 • Medications known to cause Torsade's des Pointes² |
| Supplements |
| 
 • Fish oil • Vitamin E preparations |
| P-gp Substrates |
| 
 • P-gp substrates with narrow therapeutic index (eg, Digoxin) |
| Anticoagulants and Antiplatelet Agents³ |
| 
 • Other anticoagulants then listed in Table 19 • Other medication that inhibit platelet function then listed in Table 19 |
| Surgical intervention |
| 
 • held at least 3 to 7 days pre- and post-surgery depending upon the type of surgery and the risk of bleeding |

¹ For a listing of CYP3A4/5 inhibitors and inducers see [Attachment 8](#) and <http://medicine.iupui.edu/clinpharm/ddis/main-table>.

² For a listing of medications that cause QT prolongation see http://www.azcert.org/medical-pros/drug-lists/list-01.cfm?sort=Generic_name.

³ Subjects requiring the initiation of therapeutic anticoagulation therapy (other than warfarin or a vitamin K antagonist) during the course of the study should have treatment with ibrutinib held, the sponsor's medical monitor should be contacted, and ibrutinib should not be restarted until the subject is clinically stable and the re-initiation of ibrutinib is approved by the sponsor's medical monitor. Subjects should be observed closely for signs and symptoms of bleeding. No dose reduction is required when study drug is restarted.

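### Section 6.4.1 bars ibrutinib below 280 mg/day, but Attachment 7 requires 140 mg with a moderate CYP3A inhibitor, and no exception is written

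*Protocol*

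**What the plan says.** **The floor.** Section 6.4.1 opens with "Dose reduction levels for ibrutinib, if required in Section 6.4.3, are listed in Table 7". Table 7 stops at 280 mg for both starting doses. The sentence after the table reads: "Ibrutinib dose reductions below 280 mg per day are not permitted and may require discontinuation of study therapy after consultation with the Sponsor".

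**The interaction rule.** Section 9.4 sends sites to Attachment 7: "Instructions for medications to be used with precaution are also provided in" that attachment. For a moderate inhibitor, Attachment 7 says: "If a moderate CYP3A inhibitor must be used, reduce ibrutinib to 140 mg for the duration of the inhibitor use". For a strong inhibitor whose benefit outweighs the risk, it says to "reduce the ibrutinib dose to 140 mg or withhold treatment temporarily (for 7 days or less").

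**Going back up.** Section 6.4 states: "The dose adjustments are applicable to all subsequent treatment cycles". Section 6.4.1 makes a return to the earlier, higher dose subject to consultation with the sponsor. Attachment 7 ties the moderate-inhibitor reduction to the period of inhibitor use but names no dose to resume.

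**Supporting tables.** Table 6 lists prescribed doses of 280, 420 and 560 mg only, although capsules are 140 mg (Section 15.1). SAP Section 3.4 names 280 mg/day as the only reduction level for CLL/SLL, and 420 and 280 mg/day for FL, DLBCL and Richter syndrome.

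**The concern.** A site that gives 140 mg as Attachment 7 directs breaks the wording of Section 6.4.1. A site that keeps to Section 6.4.1 gives at least twice the dose that Attachment 7 requires, or raises with the sponsor the discontinuation of a subject whom Attachment 7 would keep on treatment. Under Section 6.1, study therapy covers both drugs, and under Section 6.4 a recommendation to discontinue it applies to both. A drug interaction with ibrutinib could therefore also cost the subject nivolumab.

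The situation is foreseeable. Section 8.10 says that antimicrobial prophylaxis "is permitted and should be considered in subjects who are at increased risk for opportunistic infections". Attachment 7 lists fluconazole, voriconazole and ciprofloxacin among the moderate inhibitors.

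**Working it through.** **Step 1. Can a subject meet both rules?** Exclusion criterion 5 covers strong CYP3A inhibitors only. Table 19 (prohibited medications) does not list CYP3A inhibitors. Table 20 puts strong and moderate inhibitors under avoid or use with caution. A subject can therefore be on a moderate inhibitor during study treatment.

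**Step 2. Which cases can comply with both sections?**

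| Case | Attachment 7 | Within the 280 mg floor? |
|---|---|---|
| Strong inhibitor, 7 days or less | 140 mg or hold | Yes, by holding |
| Strong inhibitor, more than 7 days | 140 mg (a hold is limited to 7 days) | No |
| Moderate inhibitor, any duration | 140 mg (no hold offered) | No |

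**Step 3. Gap between the dose rules.** 280 / 140 = 2. If the dose is left unreduced, 420 / 140 = 3 and 560 / 140 = 4.

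**Step 4. What the gap means for exposure.** Attachment 7 reports a maximal AUC ratio of at most "2-fold in 37 patients treated with mild and/or moderate CYP3A inhibitors", compared with 76 patients not on inhibitors. Take the upper figure of 2 and assume that AUC is proportional to dose:

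relative AUC = 2 × dose given / uninhibited starting dose

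| Dose given with inhibitor | Relative to 420 mg start | Relative to 560 mg start |
|---|---|---|
| 140 mg | 2 × 140 / 420 = 0.67 | 2 × 140 / 560 = 0.50 |
| 280 mg | 2 × 280 / 420 = 1.33 | 2 × 280 / 560 = 1.00 |
| Unreduced | 2 × 420 / 420 = 2.00 | 2 × 560 / 560 = 2.00 |

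Each entry is an upper bound, because 2-fold is the reported maximum. The 24- and 29-fold increases in the protocol are for ketoconazole, a strong inhibitor, and are not used here.

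**Step 5. The return dose.** Read literally, the Section 6.4 sentence on later cycles carries a 140 mg adjustment forward. Attachment 7 ends the moderate-inhibitor reduction when the inhibitor stops. Section 6.4.1 requires a consultation before the dose goes back up. No section says which of the three governs.

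**The case against.** The strongest reply is that the rules have different scopes. The Section 6.4.1 lead-in points to Section 6.4.3, which deals only with toxicity. After giving the interaction dose, Attachment 7 adds that toxicity should be monitored and the dose modification guidance followed as needed, which treats toxicity reductions as a separate layer. On that reading the specific interaction rule governs and only a clarifying clause is missing. This is probably what was intended. But the lead-in qualifies the Table 7 levels, whereas the prohibition is a separate sentence without qualification.

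Other points on that side:

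- *Sponsor contact.* Section 9 requires the sponsor to be notified when prohibited therapies are given and cites CYP3A inhibitors as an example. Section 18.1 requires contact before a departure from the protocol, except in emergencies. This mitigates the risk, but neither section sets the dose, and the Section 9 example does not match Tables 19 and 20.
- *Attachment 8.* Section 1.2.3 cites it for guidance on CYP3A inhibitors, and it was not in the text available for this review. It could repeat dosing advice. Section 6.4.1 would still contain no exception and no pointer to it.
- *Return dose.* The natural reading of Attachment 7 is that the reduction ends with the inhibitor. That is fair, and it makes this the weaker part of the point.
- *Size and frequency.* Moderate inhibitors are to be avoided and alternatives considered first, and Section 8.10 names no drug. The protocol reports no meaningful increase in toxicity in 66 patients on moderate or strong inhibitors. An AUC of 1.33 times a 420 mg start equals that of 560 mg (560 / 420 = 1.33), which is the planned cohort A2 dose. All of this stands, and it limits the harm.

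**Conclusion.** The point holds. As written, no ibrutinib dose complies with both sections for a subject who must take a moderate CYP3A inhibitor, or a strong one for more than 7 days. The objections bear on intent, mitigation and size; none supplies the missing exception.

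The rules differ 2-fold in dose. For moderate inhibitors the exposure effect of following the 280 mg floor is modest: at most 1.33 or 1.00 times the uninhibited AUC of a 420 or 560 mg start. This rests on dose-proportional AUC and on the protocol's 2-fold upper figure, which pools mild and moderate inhibitors.

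Sample size, error rates and efficacy analyses are untouched. SAP Section 3.4 already summarises total dose, dose intensity and reasons for reduction. Amendment 7 states that the primary and secondary objectives had been analysed by then, so the benefit now is to subjects still taking ibrutinib. The change should be made because the conflict concerns patient dosing and costs almost nothing to remove.

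**What to change.** 1. Add to Section 6.4.1:

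 > The 280 mg floor and Table 7 apply only to toxicity reductions under Section 6.4.3. Temporary reduction to 140 mg for CYP3A inhibitor use under Attachment 7 is permitted; the prior dose is resumed when the inhibitor is stopped.

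2. In Section 6.4, exempt interaction-related reductions from the sentence that carries dose adjustments into all later cycles.
3. Add a 140 mg (1 capsule) row to Table 6.
4. Optionally, label interaction-related periods at 140 mg in the SAP Section 3.4 exposure table, so that they are not read as toxicity reductions.

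The sponsor should confirm the resumption dose when adopting the wording. The cost of items 1 to 3 is two sentences, one clause and one table row, with no new data collection or analysis.

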1. INTRODUCTION

This is a Phase 1/2a Study to Evaluate the Safety, Pharmacokinetics, Pharmacodynamics, and Preliminary Efficacy of the Combination of Ibrutinib with Nivolumab in Subjects with Hematologic Malignancies. There are two parts of this study. Part A (Dose Optimization Cohorts) is to determine whether ibrutinib and nivolumab can be safely combined and to establish the recommended Phase 2 dose (RP2D) for this combination in subjects with hematological disorders. Part B (Expansion Cohorts) is to determine the preliminary activity of the ibrutinib/nivolumab combination regimen in subjects with CLL/SLL with del 17p or 11q (Cohort B1), FL (Cohort B2), DLBCL (Cohort B3), and Richter syndrome (Cohort B4) in comparison to historical results.

This statistical analysis plan (SAP) contains definitions of analysis sets, derived variables, and data handling rules, and statistical approaches for the evaluation of safety, preliminary efficacy activities, and pharmacokinetics. Biomarker analysis will be included and described in this document.

1.1. Trial Objectives

The preliminary clinical activity of ibrutinib in combination with nivolumab in each disease type of part A and B in the all-treated population will be explored via the following endpoints unless otherwise stated: objective response rate [PR(+L) or better], progression-Free Survival (PFS) and overall survival (OS), duration of response (DOR) and duration of stable disease (DOSD) will be evaluated if there are sufficient data for responders for each disease-specific cohort A1, A2, B1, B2, B3 and B4 on the all-treated population. Furthermore, objective response rate [PR(+L) or better] will also be explored on the response-evaluable population, if deemed necessary. In addition, the safety profile of the ibrutinib and nivolumab combination regimen will be evaluated and the pharmacokinetic profile of ibrutinib and nivolumab compared with existing single-agent treatment data; and the potential relationships between ibrutinib and nivolumab metrics of exposure with relevant clinical or biomarker information will be characterized and explored.

1.2. Trial Design

This is an open-label Phase 1/2a study, which consists of Part A (Dose Optimization Cohorts A1 and A2) and Part B (Expansion Cohorts B1, B2, B3 and B4). In the context of this study, a treatment 'cycle' is defined as a course of treatment of 14 days starting with the intravenous administration of nivolumab on Day 1 of each cycle along with once daily oral intake of ibrutinib on all days.

It is anticipated that approximately 158 subjects for both Parts A and B would be enrolled.

Part B (Dose Expansion Cohorts) will be open for enrollment after the RP2D is determined in Part A. In Part B, further assessment of the RP2D will be explored in 4 subject populations to further evaluate the safety and clinical activity of ibrutinib in combination with nivolumab. During the expansion period, subjects with CLL/SLL with del 17p or 11q (Cohort B1), FL (Cohort B2), DLBCL including FL transformed into DLBCL (transformed DLBCL) (Cohort B3), and Richter syndrome (Cohort B4) will be enrolled. Approximately 35 subjects will be

enrolled in each of the expansion cohorts. The subjects will be treated at the RP2D level selected to further assess the safety, pharmacokinetics, pharmacodynamics, pharmacogenomics, and activity of the combination.

The median duration of study therapy is expected to be approximately from 2 (DLBCL) to 15 (CLL) months.

The End-of-Treatment Visit will occur within 30 days after the last dose of ibrutinib or nivolumab, whichever treatment occurred last.

During the Follow-up Period, long-term safety, survival status, disease progression, subsequent anticancer therapy, and occurrence of other primary malignancy data will be collected. During the Follow-up Period, subjects should be followed for safety up to 30 days after the last dose of ibrutinib or 100 days after the last nivolumab infusion, whichever is later. The safety includes adverse event reporting and laboratory assessments (at the first follow up). Thereafter Follow-up visits will be completed approximately every 3 months until death or the end of study. Subjects who have developed treatment-related Grade 3 or higher toxicity at the end of treatment will be assessed until recovery to Grade ≤ 1 or baseline, deemed irreversible, or until end of study. Adverse events leading to discontinuation will be followed up until resolution or return to baseline, or end of study, whichever occur first.

The primary analysis of the study will be performed 6 months after the last subject has received the first dose of study medication, or earlier if that subject discontinues study therapy. After the cut off for primary analysis, subjects who are receiving study treatment can continue treatment per protocol until progression, unacceptable toxicity, withdrawal of consent, or other reason as listed in protocol Section 11.2. End of study will be defined as the time when all subjects have completed the End-of-Treatment Visit and have been followed for safety up to 100 days post nivolumab as the last study assessment.

1.3. Statistical Hypotheses for Trial Objectives

This study will evaluate and describe whether ibrutinib combined with nivolumab can result in an overall response rate of more than 20% in each cohort of part B (i.e., dose expansion, cohorts B1, B2, B3 and B4), respectively.

1.4. Sample Size Justification

The sample size is calculated based on the following assumptions:

- The overall response rate under null hypothesis is 20%
- The overall response rate under alternative hypothesis is at least 38%
- The probability to mistakenly rejecting the null hypothesis when it is actually true is 0.1 (one-sided).
- The probability to correctly rejecting null hypothesis when alternative hypothesis is true is at least 0.8

Under the above assumptions, the study will enroll approximately 35 subjects to get at least 32 response evaluable subjects in each cohort of Part B (Cohorts B1, B2, B3, and B4).

2. GENERAL ANALYSIS DEFINITIONS

2.1. Analysis Cohorts

Disease type cohort is defined as: cohort of patients grouped by disease type of CLL, SLL, DLBCL, transformed DLBCL, (i.e., FL transformed to DLBCL), DLBCL overall (include both DLBCL and transformed DLBCL) Richter Syndrome from both Part A and B, unless otherwise stated. Study cohort is referring to cohorts A1, A2, B1, B2, B3 and B4.

2.2. Visit Windows

Visit window will be based on phases and cycles:

(For the purposes of this study, ‘study drug’ or ‘study therapy’ or “study treatment” refers to both ibrutinib and/or nivolumab).

Screening: Up to 28 days before the start of any study treatment.

Treatment: Between the date of first administration of study therapy and the date of the last dose of study drug. The treatment stage will be subdivided by cycles. Each cycle is 14 days, starting from the first dose of study drug. The end date of the last cycle is the date of the last dose of study drug received during the study.

End of treatment: within 30 days after the last dose of ibrutinib or 100 days after the last nivolumab. The assessments performed during the ‘End of treatment visit’ will be included in this End of treatment phase.

Follow-up: After the end of treatment till the last assessment for the last subject in the study (e.g. the last follow-up visit or death).

Baseline assessment is defined as the last non-missing results on or before the first dose of study therapy.

1. Cycle-based analysis may be performed for safety parameters during the treatment up to date of last dose of ibrutinib + 30 days, and last dose of nivolumab +100 days. For the analysis of laboratory measurement by cycle, the mean values within each cycle will be used. For the analysis of laboratory grade by cycle, the worst grade within each cycle will be used.

Assessments will be presented chronologically by cycle day or study day, which are defined as the follows:

Day 1 = date of first dose of study drug / Cycle 1 day -7 (subjects with run-in)

Study Day (if on or after date of first dose) = assessment date – date of first dose +1

Study Day (if before date of first dose) = assessment date – date of first dose

Cycle Day = assessment date – date of first dose for the cycle +1

